6.4.4 Follow up visit (Visit 8)

Patients will return to the site 14 ± 2 days after their last dose for a follow up visit.

The following assessment/information will be performed/ recorded:

- Conduct physical exam, 12-lead ECG, and vital sign (temperature, pulse rate, blood pressure) assessments.
- Check medical history

- Check prior and concomitant medications
- Independent dermatologist should perform PASI and BSA evaluation in addition to Principal Investigator (PI) or Co-Investigator (Co-I)
- DLQI questionnaire should be filled by the patient
- Photographs of the designated lesions should be taken.
- AE assessment
- Clinical laboratory tests for follow up visit (as mentioned in Table 6)
- Urine pregnancy test for females of childbearing potential only (Beta-HCG)

For patients who are withdrawn from the study for any reason, withdrawal procedures as defined in Section 7.4 will be followed.

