7.4 Withdrawal Procedures

If a patient is withdrawn from the study, the primary reason for withdrawal must be recorded in the eCRF. If a patient is withdrawn during the study period after dosing, all safety assessments (e.g. AEs, vitals, ECG, laboratory assessments etc.) according to "End of Treatment" (Week 12 ± 4 days) visit should be performed. Patient will be asked to come 14 ± 2 days after last dose for follow up visit assessments according to study activities **Table 1** If a patient is withdrawn before study drug administration, then safety assessments is not required.

The last date of study drug administration must be documented.

Appropriate follow-up of all withdrawn patients will be performed, as required. If a withdrawn patient does not follow up, then adequate attempts to contact the withdrawn patient must be documented before declaring a patient 'Lost to Follow up'.

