11.4.1.3 Handling of missing values

The last observation carried forward method will be applied to all efficacy measurements (PASI score, IGA mod 2011 score, DLQI score etc.) that are missing for the respective visits when at least one post-baseline assessment is available.

If all post baseline efficacy values are missing for one efficacy parameter then these missing values will not be imputed and this patient will be removed from the analysis

of the corresponding variable, i.e. it might be that the number of patients providing data for one variable is smaller than efficacy population.

For patients who dropped out during study treatment period due to any reason, data from the last efficacy assessment will be considered for the primary endpoint and other secondary efficacy endpoints relevant at other future time-points as per Last Observation Carried Forward (LOCF) approach. Following the intent-to-treat principle for patients who prematurely discontinue treatment, but who are observed in the follow-up period, efficacy data collected in follow-up periods will be linked to planned but missed study visits as well. Detailed imputation schemes will be described in SAP.

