#### 4.3.4 Efficacy population

Efficacy population will include patients who

- have a valid baseline and at least one post-baseline (follow up) assessment for
- PASI score by the independent dermatologist or withdrawal is associated with lack of effect by the patient before post-baseline assessment.
- do not have any major protocol or inclusion/exclusion violations,

Efficacy population will provide sample for analysis of primary, secondary and exploratory endpoints. For patients who dropped out during study treatment period due to any reason, data from the last efficacy assessment will be considered for the primary endpoint and other secondary efficacy endpoints relevant at other future time-points as per Last Observation Carried Forward (LOCF) approach.

Efficacy data collected solely based on the photographs without on-site examination by the investigator/independent dermatologist will not be considered for the analysis and this data will also be imputed with LOCF approach.

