#### 5.4 Methods for Withdrawals, Missing Data, and Outliers

In case of a patient's withdrawal from the study without any major protocol deviation, its values on subsequent visits will be considered missing.

The last observation carried forward (LOCF) method will be applied to all efficacy measurements (PASI score, IGA mod 2011 score, DLQI score etc.) when at least one post-baseline assessment is available. If all post baseline efficacy values are missing for one efficacy parameter then these missing values will not be imputed and this patient will be removed from the analysis of the corresponding variable, i.e. it might be that the number of patients providing data for one variable is smaller than efficacy population. If withdrawal prior to first post-baseline assessment is considered due to lack of effect of the study drug by the investigator, then the respective patient will be considered as non-responder in PASI and IGA responder analysis, and no change (i.e. post-baseline difference of 0) will be considered for percent or absolute change in PASI, IGA or DLQI parameters.

For missing safety variables, when repeat assessment data is available for the respective visit, then these repeat assessment data will be imputed. E.g. The hematology parameters are not available for Visit 4 for any patient and repeat hematology assessment is done prior to next scheduled visit, then hematology parameters during Visit 4 will be replaced with repeat assessment parameters. However, no values will be replaced if the parameter value is available. For example, if only ALT and AST are not available for a specific visit in biochemistry panel and repeat assessment prior to next visit is done with all liver function tests (ALT, AST, ALP, bilirubin, etc.), then only ALT and AST values will be replaced and other liver function values will not be replaced.

For the efficacy variables (PASI score, IGA mod 2011 score, DLQI score), no observed values will be considered as outliers. For safety parameters like vital signs, lab parameters etc., any value which is out of range will be summarized as observed. However, it will be checked whether it is a normal or abnormal finding and will be

	JSS Medical Research India Private Limited Data Management		
Title: Statistical Analysis Plan-Module I			
SOP Number: JSS-DM-BIS-01	Current Version Number: 1.0	Previous Version Number: Nil	Document Date: 25MAR2021

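### LOCF sets Week 12 PASI 75 status for some dropouts and no planned PASI 75 analysis varies that rule; off-treatment follow-up scores and the MMRM code also need one clear rule

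*SAP*

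**What the plan says.** **Missing data for PASI 75.** SAP 4.3.4 gives the dropout rule: "dropped out during study treatment period due to any reason, data from the last efficacy assessment will be considered for the primary endpoint". It extends this to later secondary time points, under LOCF. SAP 5.4 adds: "The last observation carried forward (LOCF) method will be applied to all efficacy measurements", provided one post-baseline score exists. Four groups fall outside LOCF:

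- rescued patients are treatment failures (protocol 8.13, SAP 4.6);
- patients who withdraw for lack of effect before any post-baseline score are non-responders (SAP 5.4);
- other patients with no post-baseline score are removed (SAP 5.4);
- patients with major deviations are outside the efficacy population (SAP 4.3.4).

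SAP 7.1 compares each dose with placebo by chi-square or Fisher's exact test. Its one sensitivity analysis is a CMH test adjusted for site and baseline PASI.

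**Scores after stopping.** At withdrawal, protocol 7.4 asks for "all safety assessments (e.g. AEs, vitals, ECG, laboratory assessments etc.) according to" the end-of-treatment visit. The patient is then asked to return 14 ± 2 "days after last dose for follow up visit assessments according to study activities". At that visit "Independent dermatologist should perform PASI and BSA evaluation" (protocol 6.4.4). Protocol 11.4.1.3 says that for patients who stop treatment early but are still observed, "efficacy data collected in follow-up periods will be linked to planned but missed study visits as well", and that "Detailed imputation schemes will be described in SAP". SAP 5.4 says of a patient who withdraws that "its values on subsequent visits will be considered missing".

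**Continuous secondary endpoints.** SAP 7.2 names an ANCOVA for each endpoint. It then sets out a model that it calls MMRM ANCOVA, with baseline, treatment, visit and visit-by-treatment terms and an unstructured covariance (AR(1) if that fails to converge). SAP 6.0 gives a PROC MIXED template under the same name.

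**The concern.** A patient who reaches PASI 75 at Week 4 or 8 and then leaves for an adverse event or by choice counts as a Week 12 responder, unless rescued or excluded. With about 30 patients per arm, each such patient is worth 3.3 points (1/30) of the arm's response rate. The planned output would not show how many responders were carried forward or whether the conclusion depends on them. SAP 1.0 says that the results may support a sample-size change, publication or regulatory submission.

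The follow-up clauses add a second problem. Two written rules can place one withdrawn patient in opposite categories.

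For the continuous endpoints, LOCF-filled data in a repeated-measures model are treated as if they had been observed, and the template would not run the model described.

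**Working it through.** **1. The plan's own figure.** Inputs (SAP 5.1, protocol 11.1): 7% versus 35%, one-sided 0.05, 25 evaluable per arm. Pooled normal approximation:

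z = [0.28·√25 − 1.645·√(2·0.21·0.79)] / √(0.07·0.93 + 0.35·0.65) = (1.400 − 0.948)/0.541 = 0.837, so power is 79.9%. The stated 80% reproduces.

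**2. How many statuses LOCF can set.** 30 × 0.15 = 4.5 and 30 × 0.20 = 6 dropouts per arm. This is an upper bound for dropouts, because the four groups listed above are subtracted and the documents do not give their size. SAP 4.3.4 also applies LOCF to photograph-only assessments, which this bound does not count.

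**3. Sensitivity of the result to recoding.** The planned rates on 30 per arm give about 10/30 versus 2/30. Both tests are shown because SAP 7.1 names both without a selection rule. Placebo is held at 2/30.

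| Active | Fisher, two-sided | Chi-square, two-sided | Fisher, one-sided | Chi-square, one-sided |
|---|---|---|---|---|
| 10/30 | 0.021 | 0.010 | 0.011 | 0.005 |
| 9/30 | 0.042 | 0.020 | 0.021 | 0.010 |
| 8/30 | 0.080 | 0.038 | 0.040 | 0.019 |
| 7/30 | 0.145 | 0.071 | 0.073 | 0.035 |
| 6/30 | 0.254 | 0.129 | 0.127 | 0.064 |

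(Chi-square is uncorrected.) From 10/30, recoding one responder changes nothing. At two-sided 0.05, Fisher needs two recodes and chi-square three. At one-sided 0.05, they need three and four. Recoding placebo responders works the other way.

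**4. How often LOCF and non-responder imputation (NRI) would disagree.** Exact enumeration with n = 30 per arm, dropout d = 0.15 to 0.20, and completers responding at 35% and 7%. Assume that a share q of active dropouts and a share r of placebo dropouts are carried forward as responders. Per patient:

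- P(completer and responder) = p(1 − d), counted by both rules;
- P(carried responder) = q·d in active or r·d in placebo, counted by LOCF only.

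| q (r) | Disagree on two-sided p<0.05, Fisher | Chi-square |
|---|---|---|
| 0 (0) | 0% | 0% |
| 10% (0-2%) | 5.4-8.4% | 4.1-6.8% |
| 20% (0-5%) | 10.6-14.6% | 7.7-11.6% |
| 35% (7%) | 16.5-21.2% | 12.5-15.9% |

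The last row is the case in which dropouts respond like completers. The active rate under LOCF exceeds that under NRI by 100·q·d points, at most 35 × 0.20 = 7.0. At one-sided 0.05, the last row becomes 13.9-18.0% (Fisher) and 8.9-11.6% (chi-square).

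**5. Can a follow-up score fall in the Week 12 window?** Week 12 is Day 84 ± 4, that is Day 80-88. The follow-up visit is 12 to 16 days after the last dose. A last dose from Day 80 − 16 = 64 to Day 88 − 12 = 76 can therefore place it there. An invented patient shows the effect: baseline PASI 20, Week 8 PASI 5, last dose Day 70, follow-up on Day 84 with PASI 8.

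- SAP 5.4 carries 5 forward: (20 − 5)/20 = 75%, a responder.
- Protocol 11.4.1.3 links 8 to the missed Week 12 visit: (20 − 8)/20 = 60%, a non-responder.

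SAP 7.3 also analyses Weeks 6 and 14 without saying to which week an early follow-up score belongs.

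**6. Model against template.** SAP 7.2 needs baseline, treatment, visit and visit-by-treatment as fixed effects, with a within-patient covariance. The template has one fixed effect and places the response variable in CLASS and RANDOM. It has no REPEATED statement, subject, covariance type, baseline or fixed treatment-by-visit term, so it cannot fit the model in SAP 7.2.

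**The case against.** LOCF was prespecified, this is a proof-of-concept trial, and every value of q above is assumed. That stands: the documents give no dropout reasons. A reader might infer that LOCF decides most dropouts, or that it inflates the treatment effect. Neither is supported. The excluded groups could be large: prohibited medication leads to discontinuation (protocol 8.11), and both it and non-compliance are deviations listed in SAP 4.3.5. Carried-forward placebo responders would also shrink the difference.

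The sample size uses one-sided 0.05, under which the result is less fragile by one recode for each test. The two-sided figures follow the hypotheses in SAP 7.1 and the 0.05 threshold in SAP 9.1.

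A reader might say that the MMRM has no input rule. Read literally, it has one: SAP 5.4 applies LOCF to everything. The objection is to the rule, not to its absence. Nor are ANCOVA and MMRM shown to be rival analyses, since the shared label suggests that they may be one model. The template is a placeholder and does contain an interaction, but only in RANDOM.

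On follow-up scores, the protocol clause concerns stopping treatment and SAP 5.4 concerns withdrawal from the study. The two overlap, because protocol 7.4 brings withdrawn patients back for the follow-up visit. Reading that visit into SAP 5.3.3 (the last value before the end-of-treatment visit) is possible but strained. What stands is that the protocol defers the detail to the SAP, and the SAP contains no linking rule.

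Rescue is largely settled: protocol 8.13 and SAP 4.6 agree on treatment failure. Only the synopsis, which joins failure with LOCF for the primary endpoint, and the value for continuous endpoints remain open.

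**Conclusion.** The point holds in this form. LOCF sets Week 12 PASI 75 status for at most 4.5 to 6 of 30 dropouts per arm at the planned dropout rate, and no planned PASI 75 analysis shows what depends on it. The consequence ranges from none, if no dropout is carried forward as a responder, to disagreement with NRI in 16.5-21.2% (Fisher) or 12.5-15.9% (chi-square) of trials if dropouts respond like completers. These figures assume the planning rates, 30 per arm and two-sided 0.05, and do not model removals from the efficacy population.

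The follow-up rule and the MMRM template are written inconsistencies and need no assumption to establish. The MMRM issue affects secondary endpoints only, and the rescue wording is minor. Overall this is something the sponsor should correct. It does not invalidate the primary analysis.

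**What to change.** 1. Keep LOCF as the primary rule. Prespecify NRI at Week 12 for PASI 75 as a sensitivity analysis (and, if wanted, for the other Week 12 responder endpoints). Tabulate by arm how many Week 12 statuses are observed, carried forward or set as failure.
2. State that the MMRM uses observed data without LOCF, and whether it is the ANCOVA named for each endpoint. Correct the code to baseline, treatment, visit and treatment-by-visit, with REPEATED visit / SUBJECT=patient TYPE=UN and the AR(1) fallback already in SAP 7.2.
3. Reconcile protocol 11.4.1.3 with SAP 5.3.3, 5.4 and 7.3, so that one rule says whether a follow-up score after discontinuation counts, and for which week.
4. Minor: align the synopsis with protocol 8.13 and SAP 4.6 on the analysis value of rescued patients (failure for responder endpoints), and state the value for continuous endpoints.

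The cost is SAP and synopsis wording, one code template and one extra table set. It needs no added patients or visits, and the primary analysis loses no power. The documents do not show whether unblinding has taken place. If it has, the added analyses should be labelled post hoc, in line with SAP 1.0.

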#### 4.3.5 Major Protocol Deviations

The protocol deviations in the study will be evaluated on a case-to-case basis and will be categorized as major or minor. A major protocol deviation is defined as any deviation that may affect the efficacy outcome or patient's safety. Subjects having major protocol deviation will be finalized prior to the soft lock.

Following are some protocol deviations.

1. Violation of major inclusion/ exclusion criteria assessment

**JSS Medical Research India Private Limited  
Data Management**

**Title: Statistical Analysis Plan-Module I**

SOP Number:  
JSS-DM-BIS-01

Current Version Number: 1.0

Previous Version Number: Nil

Document Date:  
25MAR2021

2. Use of prohibited concomitant medication
3. Treatment non-compliance
4. Non-compliance/non-assessment of study procedure
5. Visit out of the window period

#### 4.3.6 Pharmacokinetic (PK) Population

The Pharmacokinetic Population includes all patients in the study who receive any dose of AUR101 and provide samples for PK analysis.

#### 4.4 Schedule of Visits and Procedures

There will be seven scheduled visits and one follow up visit in the study mentioned as below:

- ☐ Screening visit (Up to Day -14)
  - ☐ Visit 2: Randomization visit (Day 1)
  - ☐ Visit 3: Week 2  $\pm$ 2 days
  - ☐ Visit 4: Week 4  $\pm$ 2 days
  - ☐ Visit 5: Week 6  $\pm$  2 days
  - ☐ Visit 6: Week 8  $\pm$ 2 days
  - ☐ Visit 7: (End of Treatment): Week 12 $\pm$ 4 days
- Follow-up visit: 14  $\pm$ 2 days after last dose

All the procedures that will be conducted in different visits are shown in table 3.

**Title: Statistical Analysis Plan-Module I**

 SOP Number:  
 JSS-DM-BIS-01

Current Version Number: 1.0

Previous Version Number: Nil

 Document Date:  
 25MAR2021

**Table 3. Study Activities**

Assessment	Screening visit (Up to Day -14)	Treatment Period						Follow-up visit: 14 ± 2 days after last dose
		Visit 2: Randomization visit (Day 1)	Visit 3: Week 2 ± 2 days	Visit 4: Week 4 ± 2 days	Visit 5: Week 6 ± 2 days	Visit 6: Week 8 ± 2 days	Visit 7 (End of Treatment): Week 12 ± 4 days	
Informed Consent	X							
Demographics	X							
Height (Only at Screening), BMI (only at screening), weight	X	X		X		X	X	
Medical history	X	X	X	X	X	X	X	X
Menstrual history in females	X							
Prior/concomitant medication check	X	X	X	X	X	X	X	X
Physical examination	X	X	X	X	X	X	X	X
Vital signs a	X	X	X	X	X	X	X	X
QuantiFERON TB-Gold test b	X							
Inclusion & exclusion criteria check	X							
Inclusion & exclusion criteria verification		X						
12 lead ECG	X							X
Randomization		X						
Photographs of lesions		X	X	X	X	X	X	X
Blood sampling for PK c				X				
Clinical laboratory tests (Haematology, Biochemistry)	X	X		X		X	X	X
Urinalysis		X					X	
Viral Serology	X							
PASI score, IGA by independent evaluator and Investigator	X	X	X	X	X	X	X	X
DLQI		X	X	X	X	X	X	X
IP dispense d		X	X	X	X	X		
IP return and compliance check			X	X	X	X	X	

**Title: Statistical Analysis Plan-Module I**

SOP Number: JSS-DM-BIS-01	Current Version Number: 1.0	Previous Version Number: Nil	Document Date: 25MAR2021
------------------------------	-----------------------------	------------------------------	-----------------------------

Assessment	Screening visit (Up to Day -14)	Treatment Period						Follow-up visit: 14 ± 2 days after last dose
		Visit 2: Randomization visit (Day 1)	Visit 3: Week 2 ±2 days	Visit 4: Week 4 ±2 days	Visit 5: Week 6± 2 days	Visit 6: Week 8 ±2 days	Visit 7 (End of Treatment): Week 12 ±4 days	
AE check		X	X	X	X	X	X	X
Pregnancy teste	X	X		X		X	X	X

AE = adverse event; ECG = electrocardiogram; PK = pharmacokinetic, IP= Investigational product, PASI=Psoriasis Area and Severity Index, IGA= Investigator Global Assessment

a vital sign includes body temperature, blood pressure and pulse rate

b Patients who are positive by QuantiFERON TB- Gold test, should undergo further workup according to investigator opinion (like Chest X-ray, CT scan of chest or any other locally acceptable method) to rule out active tuberculosis.

c Only in subset of approximately 25 patients

d As directed by IWRS; IP may be dispensed on additional or fewer days, as required by logistics

e Serum pregnancy test at screening, and urine pregnancy test at other visits will be done for women of childbearing potential only

#### 4.5 Permitted therapy for psoriasis

Only bland emollients or shampoos (for scalp psoriasis) will be allowed during the study participation. No active drug (topical or systemic) affecting psoriasis will be allowed during the treatment period.

#### 4.6 Rescue Medication

Rescue medication can be given if patient’s PASI score is increasing by at least 50% from baseline level at or after 6 weeks of therapy. In addition to above, if a patient has intolerable symptoms from psoriasis, then any available medication, including any biologic medications, such as secukinumab or adalimumab, can be administered as rescue medications.

Patients who receive rescue treatment during the study treatment period will be considered treatment failures for the purpose of efficacy analysis. To conduct efficacy and safety assessments (e.g. disease severity scores, safety labs) immediately before administering any rescue treatment. Patients who receive “Rescue Medication” will be discontinued from the trial. All such patients should be followed up after 14 ±2 days of study drug discontinuation for safety assessment.

	JSS Medical Research India Private Limited Data Management		
Title: Statistical Analysis Plan-Module I			
SOP Number: JSS-DM-BIS-01	Current Version Number: 1.0	Previous Version Number: Nil	Document Date: 25MAR2021

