If patient's PASI score increases by at least 50% from baseline level after at least 6 weeks of therapy, patient can be given rescue medication as considered appropriate according to investigator. In other situations, if medically necessary (i.e. to control intolerable psoriasis symptoms), rescue treatment for psoriasis may be provided to study patients at the discretion of the investigator after discussion with sponsor medical monitor. In addition, even within first 6 weeks of therapy, if a patient has intolerable symptoms from psoriasis, then rescue medications can be administered. The investigator can choose any available medication as rescue medication to treat psoriasis. In this case, investigator should discuss with sponsor medical monitor.

For the purpose of efficacy analysis, patients who receive rescue treatment during the study treatment period will be considered treatment failures with the last efficacy assessment deemed as Last Observation Carried Forward (LOCF) for the primary endpoint and other secondary efficacy endpoints relevant at other future time-points. Investigators should make every attempt to conduct efficacy and safety assessments (e.g. disease severity scores, safety labs) immediately before administering any rescue treatment. An unscheduled visit may be used for this purpose if necessary. **Patients who receive "Rescue Medication" will be discontinued from the trial.** All such patients

should be followed up after 14 ± 2 days of study drug discontinuation for safety assessment.

Statistical Analysis

Sample Size

AUR101 doses will be tested versus placebo with respect to the primary endpoint (PASI75 response). A sample size of 25 in each of the three arms will provide an 80% power with a one-sided Type I error of 0.05, if the true placebo response rate is 7% and the response rate on investigational arm(s) is 35%. The sample size is increased to 30 to account for \sim 15-20% drop outs over the study period.

Data analysis

The Safety Population includes all patients in the study who receive at least one dose of AUR101. Efficacy population will include patients who do not have any major protocol or inclusion/exclusion violations, have a valid baseline and at least one post-baseline (follow up) assessment for PASI score (i.e. primary end-point) by the independent dermatologist. The Pharmacokinetic Population includes all patients in the study who receive any dose of AUR101 and provide samples for PK analysis.

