8.13 Rescue Medication

If patient's PASI score is increasing by at least 50% from baseline level at or after 6 weeks of therapy, patient can be given rescue medication as considered appropriate according to investigator. In other situations, if medically necessary (i.e. to control intolerable psoriasis symptoms), rescue treatment for psoriasis may be provided to study patients at the discretion of the investigator after discussion with sponsor medical monitor. In addition, even within first 6 weeks of therapy, if a patient has intolerable symptoms from psoriasis, then rescue medications can be administered. The investigator can choose any available medication, including any biologic medications, such as secukinumab or adalimumab, as rescue medication to treat psoriasis. The choice of rescue medication is not part of the study and should be decided by the PI on an individualized assessment of the patient. With respect to the decision to use rescue medication, investigator should discuss with the sponsor medical monitor.

Considering the mechanism of action of study drug, it may take 4-6 weeks to show visible effects on the disease. Hence, investigators are advised to continue the study drug as long as possible unless the symptoms are intolerable and severely affect patient's health condition.

For the purpose of efficacy analysis, patients who receive rescue treatment during the study treatment period will be considered treatment failures. Investigators should make every attempt to conduct efficacy and safety assessments (e.g. disease severity scores, safety labs) immediately before administering any rescue treatment. An unscheduled visit may be used for this purpose if necessary. Patients who receive "Rescue Medication" will be discontinued from the trial. All such patients should be followed up after 14 ± 2 days of study drug discontinuation for safety assessment.

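### Rescued patients fall under both a treatment-failure rule and a last-observation-carried-forward rule, with no stated precedence, and scores taken after rescue are not excluded

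*SAP*

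**What the plan says.** **Failure rule.** SAP 4.6: "Patients who receive rescue treatment during the study treatment period will be considered treatment failures for the purpose of efficacy analysis". Protocol 8.13 has the same rule: "patients who receive rescue treatment during the study treatment period will be considered treatment failures". SAP 4.6 adds that these patients "will be discontinued from the trial".

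**LOCF rule.** SAP 4.3.4: "For patients who dropped out during study treatment period due to any reason, data from the last efficacy assessment will be considered". This LOCF rule covers both the primary endpoint and later secondary endpoints. Protocol 11.4.1.3 has the same provision. SAP 5.4 applies LOCF to all efficacy measurements once one post-baseline assessment exists. SAP 5.3.3 uses the last available value for anyone who does not complete treatment. None of these mentions rescue, and neither do the efficacy analyses in SAP 7.1 and 7.2.

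**Both in one sentence.** The protocol synopsis says rescued patients "will be considered treatment failures with the last efficacy assessment deemed as Last Observation Carried Forward (LOCF) for the primary endpoint", and goes on to the secondary endpoints at later time points.

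**Routes to rescue.** SAP 4.6 gives two. One is that the "PASI score is increasing by at least 50% from baseline level at or after 6 weeks of therapy". The other is intolerable symptoms, with no PASI threshold. Biologics are allowed as rescue.

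**Follow-up data.** For patients who stop early but are seen in follow-up, Protocol 11.4.1.3 links follow-up efficacy data to the planned visits they missed. It does not set aside data collected after rescue. It leaves detailed imputation schemes to the SAP.

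**The concern.** Because rescue ends participation, every rescued patient meets the conditions of both rules. One rule makes the patient a failure whatever the last score. The other takes the last score at face value, and that score can be a response. The Week 12 PASI 75 status of the same patient could therefore depend on which SAP section is programmed. The same applies to PASI 50, IGA 0 or 1 and the other responder endpoints.

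The follow-up provision adds a second problem. PASI and IGA are scheduled at the follow-up visit (Protocol Table 1), 14 ± 2 days after the last dose. A patient rescued at Week 6 would be seen at about Week 8. If that score is linked to the missed Week 8 visit and then carried to Week 12, the effect of the rescue drug is credited to the randomised arm.

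Rescue reflects inadequate control of disease, so it may well differ between arms. An ambiguity tied to rescue may therefore not cancel out in the comparison with placebo.

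**Working it through.** **Plan's own figure.** The plan states no figure about rescue. The relevant planning inputs are 7% vs 35%, one-sided 0.05, 80% power and 25 per arm raised to 30 (Protocol 11.1, SAP 5.1). With the pooled normal formula and mean rate (0.07 + 0.35)/2 = 0.21:

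n = [1.645·√(2·0.21·0.79) + 0.842·√(0.07·0.93 + 0.35·0.65)]² / 0.28² ≈ 25.1, which rounds up to 26. Power at 25 per arm is 79.9%. The stated figure reproduces, and this point does not change it.

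**Do the rules disagree?** Take a baseline PASI of 20. The patient values below are hypothetical.

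| Rescue route and score carried | Change | Failure rule | LOCF rule |
|---|---|---|---|
| PASI trigger, trigger score 30 carried | (30 − 20)/20 = +50% | non-responder | non-responder |
| Intolerable symptoms, last score 10 | (10 − 20)/20 = −50% | non-responder | PASI 50 responder |
| Intolerable symptoms, last score 5 | (5 − 20)/20 = −75% | non-responder | PASI 75 responder |
| PASI trigger, post-rescue follow-up score 5 linked to a missed visit | −75% | non-responder | PASI 75 responder |

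The rules agree in the first row and conflict in the others. An older score can also be carried. Protocol 8.13 asks for every attempt at an assessment just before rescue but does not guarantee one, and scheduled visits are four weeks apart between Weeks 8 and 12.

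**Size for a responder endpoint.** One reclassified patient moves an arm's rate by 1/30 = 3.3 points. The planned rates give about 0.35 × 30 = 10.5 active and 0.07 × 30 = 2.1 placebo responders. SAP 9.1 sets significance at p < 0.05. Two-sided p-values at 30 per arm:

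| Active vs placebo responders | Fisher | Chi-square (uncorrected) |
|---|---|---|
| 10 vs 2 | 0.021 | 0.010 |
| 9 vs 2 | 0.042 | 0.020 |
| 8 vs 2 | 0.080 | 0.038 |
| 7 vs 2 | 0.146 | 0.071 |

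One active-arm reclassification crosses 0.05 from 9 vs 2 by Fisher, or from 8 vs 2 by chi-square. From 10 vs 2 it takes two by Fisher and three by chi-square. A placebo reclassification works the other way: 8 vs 2 becomes 8 vs 1, and Fisher p falls from 0.080 to 0.026.

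**Size for a continuous endpoint.** One patient carried at +50% rather than at zero change shifts the arm's mean percent change in PASI by 50/30 = 1.7 points, in the unfavourable direction. If three patients (assumed) are carried at −30%, the shift is 3/30 × 30 = 3.0 points in the favourable direction.

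**The case against.** The best defence is that SAP 4.6 and Protocol 8.13 are specific to rescue while SAP 4.3.4 is a general dropout rule, so on an ordinary reading the specific rule governs. The synopsis can then be read coherently: failure for responder endpoints, LOCF where a number is needed. This is a reasonable reading and probably the intended one. But no section states it, and the synopsis names LOCF for the primary endpoint itself, which is a responder endpoint.

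Second, the PASI trigger cannot be established without measuring PASI, so on that route the pre-rescue score gives non-response under both rules. This stands, and it limits the PASI 75 conflict largely to patients rescued for symptoms after a large improvement. SAP 4.6 also asks for the pre-rescue assessment without the protocol's best-efforts qualifier.

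Third, the SAP does not repeat the follow-up linkage, and SAP 5.4 opens by treating values after withdrawal as missing where there was no major deviation. That lowers the risk, but the protocol provision is not withdrawn and post-rescue scores are nowhere excluded.

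Fourth, the p-values are chosen near the boundary, and rescue for lack of effect might be expected more often on placebo, where reclassification would widen the difference. Both remarks are fair. The figures show sensitivity, not a likely effect.

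A reader might also infer that failure has no value at all for the continuous endpoints. The documents do not support that: the synopsis attaches LOCF to rescued patients for secondary endpoints, and SAP 4.3.4 and 5.4 supply the value. Nor does the zero-change rule in SAP 5.4 ("no change (i.e. post-baseline difference of 0) will be considered for percent or absolute change in PASI, IGA or DLQI parameters") show unequal treatment of like cases. It covers only lack-of-effect withdrawal before the first post-baseline assessment, when there is nothing to carry.

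**Conclusion.** The concern holds as a conflict between stated rules without a precedence sentence, together with a missing exclusion of post-rescue scores. It should be corrected, but it is not a fundamental flaw. The responder conflict depends on rescue for intolerable symptoms, on an older score being carried, or on a post-rescue score being used. The documents give no rescue rate, so the number affected is unknown. It is probably small for PASI 75 and larger for PASI 50, whose threshold is easier to have met before rescue. With about 30 per arm, one patient can matter when the result is near the threshold; at 10 vs 2 it does not.

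For continuous endpoints the gap is narrower: the SAP does not confirm that carrying the last pre-rescue score is how failure is scored. LOCF is not uniformly lenient there, since a patient carried at +50% counts against the arm.

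A reader might conclude that the choice would be made after seeing the results. The documents do not show this: the trial is double-blind and programming specifications are not part of what was provided.

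**What to change.** 1. In SAP 4.3.4 and Protocol 11.4.1.3, after *due to any reason*, add *except patients who received rescue treatment*. Add the same exception, for responder endpoints, to the LOCF paragraph of SAP 5.4, where that phrase does not occur.
2. State in SAP 4.6 and 7.1 that a rescued patient is a non-responder for every binary efficacy endpoint (PASI 50, 75, 90 and 100, IGA 0 or 1, and the DLQI responder analyses) at each visit on or after rescue, whatever the last score.
3. State that efficacy assessments made after rescue are not used for imputation and are not linked to missed visits.
4. For continuous endpoints, confirm the value the synopsis already implies: the last score before rescue, carried forward. A harsher penalty can be an optional sensitivity analysis.
5. Align the synopsis with Protocol 8.13 by removing LOCF for the primary endpoint in rescued patients.

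The cost is a few sentences in the SAP and a protocol clarification, with no new data and no change to patient management. The text should be settled before the soft lock that SAP 4.3.5 sets as the deadline for finalising major deviations. The downside is a slightly lower response rate in an arm that has a rescued patient whose last score was good.
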